5.4. Suspected ARI Visit

Subjects requiring Suspected ARI Visit will be evaluated as follows:

1. Physical examination as warranted by the Investigator for any change from baseline.
2. Body weight and collection of vital signs to include blood pressure, pulse, respiratory rate and body temperature.
3. Collection of two nasopharyngeal swabs using nylon flocked dry swabs for RT-PCR.
4. Collect two nasopharyngeal swabs 24 to 36 hours later and then again 4 to 5 days later.
5. The subject will complete a FLU-PRO® symptom diary daily until he/she responds “yes” to the FLU-PRO® question, “Have you returned to your usual health?” for 3 consecutive days or until the Week 8 Visit, whichever occurs first. The daily FLU-PRO® diary will be

completed between 4:00 pm and 8:00 pm. A caregiver may assist the subject with completing the diary if needed.

6. Review and recording of concomitant medications.
7. Review and recording of adverse events/side effects.
8. Laboratory investigations for safety may be performed as warranted based upon the Investigator's judgment.
9. If a subject tests positive for a respiratory virus by RT-PCR, that subject may receive standard of care as clinically warranted by the Investigator.

Regardless of symptoms or laboratory data, the subject will continue treatment until the 6-week treatment period has ended.

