10.4. Medication Modification/Withdrawal Due to an Adverse Event

If a severe adverse reaction develops during therapy, the study medication should be discontinued, and the subject should be withdrawn from the study.

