11.2. Subject Discontinuation

Treatment will be discontinued for individual subjects for the following reasons:

1. An allergic reaction occurs or is suspected.
2. Medical conditions that may require study discontinuation in the Investigator's judgment.
3. Subject desire to discontinue participation.

In the case of an allergic reaction or other medical condition requiring subject discontinuation, appropriate treatment will be instituted by the Investigator.

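### Protocol 5.4 and SAP 1.2 continue treatment without exception, which conflicts with Protocol 10.4 and 11.2 for subjects who also meet a stopping condition at a Suspected ARI Visit

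*Protocol*

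**What the plan says.** The last line of Protocol 5.4 reads "Regardless of symptoms or laboratory data, the subject will continue treatment until the 6-week treatment period has ended". SAP 1.2, under Suspected ARI Visit, has the same sentence. Neither carries an exception or a cross-reference.

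The item just before it in 5.4 concerns virology: "If a subject tests positive for a respiratory virus by RT-PCR, that subject may receive standard of care". Two items earlier in the same list concern safety: "Review and recording of adverse events/side effects" (item 7) and "Laboratory investigations for safety may be performed as warranted based upon the Investigator's judgment" (item 8).

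Four other protocol sections bear on stopping:
- **10.4:** "If a severe adverse reaction develops during therapy, the study medication should be discontinued, and the subject should be withdrawn from the study".
- **11.2** lists three reasons for which treatment will be stopped: an actual or suspected allergic reaction (reason 1), "Medical conditions that may require study discontinuation in the Investigator's judgment" (reason 2), and the subject's own wish (reason 3).
- **10.2** has the Principal Investigator review all moderate and severe adverse events and judge whether they warrant discontinuation.
- **5.8** says the discontinuation rules are in 11.2 and sets out how subjects who leave before Week 6 are evaluated.

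**The concern.** The 5.4 sentence has no limit on its face. It sits in the section that site staff will have open when they see an acutely ill resident, and that visit includes adverse event review and may include safety laboratory tests. A subject can meet a stopping condition in 10.4 or 11.2 at the same visit, and the protocol does not say which instruction then applies.

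What is at stake is subject safety and uniform conduct. Facilities could handle the same situation differently, so exposure after illness onset and recorded discontinuations could vary by site. Under 10.4 a stop also means withdrawal from the study, so the choice of instruction can decide whether later swabs and the Week 8 antibody sample are collected.

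**Working it through.** The plan states no figure on this point, so the check compares the trigger and scope of each instruction.

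**Step 1: can the triggers coincide?** Under Protocol 5.3 and Table 5, any single lower respiratory symptom leads to a Suspected ARI Visit, and wheezing and dyspnea are both on that list. Protocol 5.2 names wheezing, trouble breathing and a suspected allergic-like reaction among the reasons to contact the study physician. A possible allergic reaction can therefore present as a Suspected ARI. Items 7 and 8 of 5.4 are a further route by which a severe reaction or another medical condition can come to light at the visit.

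**Step 2: compare by situation at the visit.**

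| Situation | 5.4, read literally | Other provision | Conflict? |
|---|---|---|---|
| ARI symptoms, RT-PCR positive or negative, no stopping condition | Continue | None triggered | No |
| Severe adverse reaction | Continue | 10.4: stop and withdraw | Yes |
| Actual or suspected allergic reaction | Continue | 11.2 reason 1: stop | Yes |
| Medical condition judged by the Investigator to require discontinuation, shown by symptoms or laboratory results | Continue | 11.2 reason 2: stop | Yes |
| Subject wishes to stop | Not addressed, since a wish is neither a symptom nor a laboratory result | 11.2 reason 3: stop | No |

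**Step 3: does any passage settle the three conflicts?** Protocol 5.8 points to 11.2 but does not qualify 5.4 and does not mention 10.4. Protocol 10.2 gives discretion but does not say that it overrides 5.4. Sections 10.4 and 11.2 do not mention 5.4. Nothing states an order of precedence.

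**Step 4: size.** Two sets of subjects must be kept apart.

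*Subjects who may come under the sentence.*
- The sample size assumptions give 0.10 × 400 + 0.02 × 400 = 48 subjects with a VRI.
- The cited 1.6 respiratory infections per person-year gives 1 − exp(−1.6 × 6/52) = 16.9%, or 1.6 × 6/52 = 18.5% without the exponential. That is about 135 to 148 of 800.
- The protocol's rounded 20% gives 160.

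*Subjects in conflict.* These must also meet 10.4 or 11.2 reason 1 or 2, and the documents give no rate for that. The nearest figure is in Protocol 1.2.4: under 1% stopped therapy because of adverse events, mostly in 5-day use. As an illustration only, assume that a stopping condition is independent of having a visit and that 17% to 20% of subjects have a visit:
- At 1%: 0.01 × 800 = 8 subjects, and 8 × 0.17 to 0.20 = about 1 to 2 in conflict.
- At an assumed 10%, for six weeks of dosing: 80 subjects, and 80 × 0.17 to 0.20 = about 14 to 16 in conflict.

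Independence probably understates the overlap, because wheezing or dyspnea can belong to both conditions. If every such subject had a visit, the counts would be 8 and 80. The proxy also leaves out subjects stopped because the respiratory illness itself worsens.

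**The case against.** The strongest reply is that the sentence, read in context, means only that an acute respiratory illness or a positive virus test does not end prophylaxis. It follows directly on the RT-PCR item, in a visit built around swabs and the symptom diary. Protocol 10 says that symptoms and complications of viral respiratory illness are not reported as adverse events, so an ordinary case would not be expected to trigger 10.4. Protocol 5.8, in the same chapter, sends sites to 11.2 and plainly expects some subjects to stop early.

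Much of this stands. The narrow reading is available and is probably the intent, and items 7 and 8 do not rule it out. It does not dispose of the point, for three reasons:
- The wording is wider than that purpose, and no passage narrows it.
- Even limited to respiratory symptoms and virology, it meets 11.2 reason 2 when a subject's respiratory illness worsens to the point where the Investigator judges that treatment should end.
- The text in Protocol 10 is a reporting convention, not a stopping rule. The symptoms it names do not include wheezing or dyspnea.

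A reader might also infer that a Grade 4 safety laboratory result sets 5.4 against a mandatory stop. The documents do not support that. Section 10.4 speaks of a severe adverse reaction, 10.2 and 11.2 reason 2 leave the matter to judgment, and the Grade 3 or 4 rule in 11.1 is a study-level stop when more than 20% of subjects are affected.

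**Conclusion.** The instructions conflict when read literally, but only for the subset of subjects at a Suspected ARI Visit who also have a severe adverse reaction, an actual or suspected allergic reaction, or a medical condition that the Investigator judges to require discontinuation.

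A reader might infer that every subject who reaches the visit faces contradictory instructions, and take 48 or 135 to 160 as the number affected. That does not follow. Reaching the visit triggers neither 10.4 nor 11.2, and those figures count expected illnesses, not conflicts. The true number cannot be derived from the documents. It is likely small, on the assumption that stopping conditions are uncommon over six weeks.

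Sample size, power, alpha and the endpoint definitions are unaffected. Randomization is within facility, so differing site practice should not by itself bias the treatment comparison. This is a wording defect on a safety matter that should be corrected; it does not put the trial's conclusions at risk. The SAP sentence is a copy within a synopsis of procedures, not a separate defect.

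**What to change.** Reconcile Protocol 5.4 and SAP 1.2 with Protocol 10.2, 10.4 and 11.2. State in 5.4 what the sentence is meant to cover (for example ARI status and RT-PCR results, if that is the intent) and how it relates to the discontinuation provisions. Use the same wording in SAP 1.2. The sponsor and its medical monitor decide which provision governs; this review takes no position on that.

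The cost is one sentence in the protocol, its copy in the SAP and a memo to sites. No procedure, visit or analysis is added. Recorded treatment discontinuations might change slightly once sites apply a single rule.

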5.5. Week 1, Week 3, and Week 6 Evaluations (± 2 days)

A study physician, nurse or other study personnel will visit each subject at Week 1, Week 3, and Week 6, and the following procedures will be performed:

1. Physical examination as warranted by the Investigator for any change from baseline.
2. Body weight and collection of vital signs to include blood pressure, pulse, respiratory rate and body temperature.
3. Week 3 and Week 6 only, collection of blood sample for laboratory safety tests, pharmacokinetics (pre-dose) and anti-SARs-CoV-2 antibodies (antibody testing at Week 6 visit only).
4. Week 3 and Week 6 only, collection of urine sample for routine urinalysis.
5. Review of compliance with study medication, collection of medication bottle with any unused medications (Week 6 visit only), and completion of the pill count log form.
6. Review and recording of concomitant medications.
7. Review and recording of adverse events/side effects and complications. Note that all adverse events and complications must be followed until their resolution or stabilization even beyond the 8-week study period.

5.6. Week 8 Evaluation (+7 days)

A study physician, nurse or other study personnel will visit each subject at Week 8 and the following procedures will be performed:

1. Physical examination as warranted by the Investigator for any change from baseline.
2. Collection of blood sample for anti-SARs-CoV-2 antibodies.
3. Review and record concomitant medications.
4. Review and record adverse events/side effects and complications. Note that all adverse events and complications must be followed until their resolution or stabilization even beyond the 8-week study period.
5. Document any infections diagnosed during the follow-up period.

5.7. Unscheduled Visit

Subjects requiring an unscheduled visit due to worsening symptoms or adverse events will be evaluated at the discretion of the Investigator as is medically warranted. Tests and/ or procedures performed at this visit may include, but are not limited to, the following:

1. Physical examination as warranted by the Investigator for any change from baseline.
2. Body weight and collection of vital signs to include blood pressure, pulse, respiratory rate and body temperature.
3. Collection of two nasopharyngeal swabs using nylon flocked dry swabs for RT-PCR.
4. Collection of blood sample for laboratory safety tests.
5. Collection of urine sample for routine urinalysis.
6. Review of compliance with study medication.
7. Review and recording of concomitant medications.
8. Review and recording of adverse events/side effects.

5.8. Study Discontinuation

Rules for discontinuation of a subject or for discontinuing the study are provided in Section 11.2. All subjects discontinued from the study before Week 6 will be evaluated at study discontinuation using the procedures described above for the Week 6 evaluation. Those discontinued after Week 6 will be evaluated as warranted by the Investigator.

5.9. Plan for Laboratory Safety Tests

A central laboratory will be used for laboratory safety testing. Blood tests will include hemoglobin, hematocrit, complete blood count (total and differential), platelet count, random blood sugar, total cholesterol, HDL, LDL, triglycerides, albumin, AST, ALT, GGT, alkaline phosphatase, bilirubin (total/direct), BUN, creatinine, sodium, potassium, chloride. Routine urinalysis will include appearance, glucose, protein, and blood.

5.10. Plan for Virology Testing and Monitoring Resistance

Blood samples collected at Baseline, Week 6 and Week 8 will be tested for anti-SARS-CoV-2 antibodies at a central laboratory using a validated assay (when such become available).

Virology testing of nasopharyngeal swab samples will be conducted as described below.

1. Collection of samples:

Two nasopharyngeal swabs will be collected from each subject at Baseline (Day 1), at each Suspected ARI Visit, 24 to 36 hours after each Suspected ARI Visit, 4 to 5 days after each Suspected ARI Visit and as warranted by the Investigator.

2. Testing of biological samples:

Each nasopharyngeal swab sample will be subjected to RT-PCR using the ePlex® Respiratory Pathogen Panel (GenMark, Carlsbad, CA) to detect influenza A (non-specific as to subtype); influenza A H1, H1N1 (2009), H3 subtypes; influenza B; RSV A

and B; parainfluenza 1, 2, 3 and 4; hMPV; adenovirus; human EV/RV; coronavirus NL63, HKU1, 229E and OC43; *Chlamydophila pneumoniae*; and *Mycoplasma pneumoniae*. The Aptima® SARS-CoV-2 Assay (Hologic, Inc, San Diego, CA) will be used to test for SARS-CoV-2.

3. Drug susceptibility testing:

If any Suspected ARI Visit nasopharyngeal swab sample is positive for a VRI, the virus will be isolated (if possible) and tested for susceptibility to tizoxanide.

4. Storage of samples: All samples collected during the study will be stored for at least 2 years for potential future testing.

5. Clinical virology laboratory for diagnostic testing:

[REDACTED]

6. Clinical virology laboratory for drug susceptibility testing:

[REDACTED]

6. RANDOMIZATION

Subjects will be randomized 1:1 by stratum to receive either NTZ or placebo. An independent third party will prepare a master randomization list and maintain the masking of the study. Subjects who qualify for the study will be assigned to treatment using centralized randomization procedures. The treatment numbers will appear on the bottles containing the masked study medication. The randomization list will be masked to study participants including Sponsor, Investigators, study monitors, statisticians, subjects and laboratory personnel. Unmasking procedures will be detailed in the Medical Monitoring Plan and Investigators will be provided instructions for unmasking.

7. DATA MANAGEMENT

7.1. Electronic Data Entry

Data will be transcribed from source documents into an electronic data capture (EDC) system.

The responsible study monitor(s) will verify data according to the study-specific Clinical Monitoring Plan either remotely or at the clinical study site. The Investigator will ensure that the data recorded are accurate and complete.

Queries emerging during data cleaning will be generated within the EDC system by data management or clinical research associates. The Investigator or his/her designee will answer the queries and update the source data, if needed.

Adverse events and comorbid conditions will be coded by data management using the latest version of the Medical Dictionary for Regulatory Activities (MedDRA). Medications will be coded by data management using the World Health Organization (WHO) Drug Dictionary.

After the last subject last visit has taken place, the database will be cleaned as necessary. As soon as the database is considered clean, it will be locked. The locked database will be used in the final statistical analysis for study reporting. Measures will be undertaken to protect subject data handled during inspections against disclosure to unauthorized third parties. Subject confidentiality will be maintained at all times.

7.2. Protocol Deviations

Protocol deviations will be documented by the Investigator, reported to the institutional review board (IRB) as appropriate, and also reviewed by the assigned clinical research associate. Deviations will be reported in the clinical trial management system or applicable EDC. Each deviation will be classified as major or minor according to the following definitions:

Major protocol deviation: A deviation that has an impact on subject safety, may substantially alter risks to subjects, may have an effect on the integrity of the study data, or may affect the subject's willingness to participate in the study

Minor protocol deviation: All other protocol deviations.

7.3. Data Quality Assurance

The accuracy and reliability of the study data will be assured by the selection of qualified Investigators and appropriate study centers, review of protocol procedures with the Investigator and associated personnel prior to the study, and by periodic monitoring visits by the Sponsor or Sponsor's representatives. Written instructions will be provided for collection, preparation, and shipment of samples.

The monitor will review the source data for accuracy and completeness, and any discrepancies will be resolved with the Investigator or designee, as appropriate.

The Sponsor will be entitled to inspect and audit the facilities used in the clinical and laboratory parts of the study, as well as to make anonymized copies of all the data files pertaining to the study. Similar procedures may also be conducted by agents of any regulatory body, either as part of a national GCP compliance program or to review the results of this study in support of a regulatory submission. The Investigator should immediately notify the Sponsor if they have been contacted by a regulatory agency concerning an upcoming inspection.

8. STATISTICAL CONSIDERATIONS

8.1. Sample Size Calculations

Recent reports of COVID-19 in long-term care facilities in the United States have suggested a high rate of transmission of the SARS-CoV-2 virus, but infection control procedures may significantly decrease transmission (McMichael et al. 2020, Kimball et al. 2020). A recent study of 264 elderly volunteers (≥ 65 years of age) reported 1.6 respiratory tract infections (not laboratory-confirmed) per person-year indicating approximately a 20% probability of respiratory tract infection over a given 6-week period (Mannick et. al, 2018). Infection control procedures in place during the period covered by this clinical trial are also expected to reduce the transmission of other respiratory viruses.

For purposes of calculating our sample size, we assume that the proportion of subjects experiencing COVID-19 over a 6-week period is 5%, the proportion of subjects experiencing any VRI is 10%, and that effective prophylaxis will reduce the rate of COVID-19 and other VRIs by 80%. Influenza prophylaxis studies of oseltamivir have resulted in approximately 80% reduction of influenza illness among residents of long-term care facilities (see Tamiflu® prescribing information).

A Cochran-Mantel-Haenszel (CMH) chi-square test stratifying by 20 LTCFs will have 92.8% statistical power to detect the difference between 5% and 1% rates of occurrence of COVID-19 over all strata at an alpha of 0.049 with a total sample size of 800, allocated equally to strata (LTCFs) and treatment groups within strata. The statistical power remains >92% when the number of LTCFs is 5, 10, 16 or 20. The CMH chi-square test has 93.9% power to detect the difference between 10% and 2% rates of occurrence of VRIs over all strata at an alpha of 0.001 with 800 subjects allocated equally to 20 LTCFs. Adjusting the stratum size to assume unequal allocation while holding the effect size and total sample size constant results in negligible changes (i.e., changes in the third significant figure) in the study power.

A sample size of 800 subjects (400 per treatment group) was selected.

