8.4. Statistical Methodology

The statistical methodology is described briefly below and will be described in detail in the Statistical Analysis Plan.

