8.4.1. Efficacy Analyses

Efficacy analyses will be based on a population consisting of all subjects randomized without a laboratory-detected viral respiratory infection at the baseline visit (intention-to-treat or ITT population).

There will be two primary efficacy analyses:

- The proportion of subjects experiencing COVID-19 in the NTZ treatment group will be compared to that of the placebo treatment group using a two-sided Cochran-Mantel-Haenszel (CMH) chi-square test ($\alpha = 0.049$).
- The proportion of subjects experiencing VRI in the NTZ treatment group will be compared to that of the placebo treatment group using a two-sided CMH chi-square test ($\alpha = 0.001$).

Secondary analyses will be performed as follows:

- Proportions of subjects experiencing hospitalization due to COVID-19 or complications thereof will be compared by treatment group using a two-sided CMH Chi-square test (unadjusted $\alpha = 0.05$).
- Proportions of subjects experiencing mortality due to COVID-19 or complications thereof will be compared by treatment group using a two-sided CMH Chi-square test (unadjusted $\alpha = 0.05$).
- Proportions of subjects (with or without symptoms) testing positive for antibodies to SARS-CoV-2 at either of the Week 6 or Week 8 visits will be compared by treatment group using a two-sided CMH Chi-square test (unadjusted $\alpha = 0.05$).

Exploratory analyses will be performed as follows:

- Proportions of subjects experiencing each of the following will be compared by treatment group using a two-sided CMH Chi-square test (unadjusted $\alpha = 0.05$): (i) hospitalization due to VRI or complications thereof; (ii) mortality due to VRI or complications thereof, (iii) acute respiratory illness (ARI), (vi) hospitalization due to ARI or complications thereof; and (v) mortality due to ARI or complications thereof.

Other analyses may be performed as outlined in the study Statistical Analysis Plan.

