### 1.3 Sample Size

Recent reports of COVID-19 in long-term care facilities in the United States have suggested a high rate of transmission of the SARS-CoV-2 virus, but infection control procedures may significantly decrease transmission (McMichael et al. 2020, Kimball et al. 2020). A recent study of 264 elderly volunteers ( $\geq 65$  years of age) reported 1.6 respiratory tract infections (not laboratory-confirmed) per person-year indicating approximately a 20% probability of respiratory tract infection over a given 6-week period (Mannick et. al, 2018). Infection control procedures in place during the period covered by this clinical trial are also expected to reduce the transmission of other respiratory viruses.

For purposes of calculating sample size, we assume that the proportion of subjects experiencing COVID-19 over a 6-week period is 5%, the proportion of subjects experiencing any VRI is 10%, and that effective prophylaxis will reduce the rate of COVID-19 and other VRIs by 80%.

A Cochran-Mantel-Haenszel (CMH) chi-square test stratifying by 20 LTCFs will have 87.1% statistical power to detect the difference between 5% and 1% rates of occurrence of COVID-19 across all strata at a two-sided alpha of 0.047 with a total sample size of 800, allocated equally to strata (LTCFs) and treatment groups within strata. The statistical

power remains >87% when the number of LTCFs is 5, 10, 16 or 20. The CMH chi-square test has 91% power to detect the difference between 10% and 2% rates of occurrence of VRIs over all strata at a two-sided alpha of 0.001 with 800 subjects allocated equally to 20 LTCFs. Both tests are insensitive to stratum size. Varying the number of subjects per stratum (LTCF) between a minimum of 8 to a maximum of 80 while holding both the effect size and total sample constant results in changes in the third significant figure of the test's power.

A sample size of 800 subjects (400 per treatment group) was selected.

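### Protocol 8.1 and SAP 1.3 state different powers for the same 800-subject design (COVID-19 92.8% against 87.1%, VRI 93.9% against 91%); neither COVID-19 figure matches the simulated power of the planned test, about 90%

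*Protocol*

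**What the plan says.** **Protocol 8.1** takes 800 subjects, 400 per group, spread equally over 20 LTCFs. It gives "92.8% statistical power to detect the difference between 5% and 1% rates of occurrence of COVID-19 over all strata at an alpha of 0.049" and adds "The statistical power remains >92% when the number of LTCFs is 5, 10, 16 or 20". For VRI it gives "93.9% power to detect the difference between 10% and 2% rates of occurrence of VRIs over all strata at an alpha of 0.001". It names the CMH chi-square test and the strata. It gives no sidedness, continuity correction or power formula.

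**Protocol 8.4.1** compares NTZ on COVID-19 with the "placebo treatment group using a two-sided Cochran-Mantel-Haenszel (CMH) chi-square test" at 0.049, and treats VRI likewise, two-sided, at 0.001. No continuity correction is mentioned. Protocol 8.4 says: "The statistical methodology is described briefly below and will be described in detail in the Statistical Analysis Plan".

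**SAP 1.3** keeps the sample size, rates, test and 20 LTCFs, but says the test "will have 87.1% statistical power to detect the difference between 5% and 1% rates of occurrence of COVID-19" at a two-sided alpha of 0.047, and that "power remains >87% when the number of LTCFs is 5, 10, 16 or 20". For VRI it gives 91% at two-sided 0.001. It names no power formula and no correction.

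**SAP 2.4** sets the final COVID-19 alpha at 0.047 if the interim efficacy review takes place and at 0.049 if it does not. The final VRI alpha is 0.001 either way.

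**SAP 4.2.1** specifies two-sided CMH tests, stratified by LTCF, with continuity correction.

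**The concern.** The two documents describe one design and one test, yet their powers differ by 5.7 points for COVID-19 and 2.9 points for VRI. The stated floors across numbers of LTCFs also differ, above 92% against above 87%. Neither text explains this, and the SAP revision history does not mention power.

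The only visible difference in inputs is the COVID-19 alpha, and 0.049 against 0.047 is far too small a change to produce such a gap. The VRI alpha is identical.

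The protocol uses these figures to support N=800. A reader such as the IRB or the IDMC cannot tell which test or method each figure describes, or which figure to rely on. Nothing in the final analysis depends on them, so what is at stake is the accuracy of the sample-size justification, not the inference.

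**Working it through.** **Inputs.** n = 400 per arm; COVID-19 5% v 1%; VRI 10% v 2% (Protocol 8.1, SAP 1.3). Alphas are 0.049 and 0.001 (Protocol 8.1, 8.4.1) and 0.047 or 0.049 and 0.001 (SAP 1.3, 2.4). Continuity correction is from SAP 4.2.1.

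**Step 1: reproduce the printed figures.** Normal approximation for two proportions, with the difference reduced by 1/n:

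power = Φ[(d − 1/n − z·se0)/se1], with se0 = √(2p̄(1−p̄)/n) and se1 = √((p1(1−p1) + p2(1−p2))/n)

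- COVID-19: d = 0.04, p̄ = 0.03, se0 = √(2×0.03×0.97/400) = 0.01206, se1 = √((0.0475 + 0.0099)/400) = 0.01198
- VRI: d = 0.08, p̄ = 0.06, se0 = √(2×0.06×0.94/400) = 0.01679, se1 = √((0.0900 + 0.0196)/400) = 0.01655
- 1/n = 0.0025

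| Endpoint, alpha | Sides | z | Power | Printed |
|---|---|---|---|---|
| COVID-19, 0.049 | one | 1.655 | 0.9284 | Protocol 92.8% |
| VRI, 0.001 | one | 3.090 | 0.9391 | Protocol 93.9% |
| COVID-19, 0.047 | two | 1.986 | 0.8708 | SAP 87.1% |
| VRI, 0.001 | two | 3.291 | 0.9105 | SAP 91% |
| COVID-19, 0.049 | two | 1.969 | 0.8746 | none |

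All four printed figures appear. Moving alpha from 0.049 to 0.047, two-sided, costs 0.8746 − 0.8708 = 0.0038, or about 0.4 of the 92.8 − 87.1 = 5.7 points. For VRI alpha contributes nothing to 93.9 − 91 = 2.9 points.

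**Step 2: could a two-sided calculation give 92.8%?** None of those tried at alpha 0.049 does: pooled uncorrected 0.9126, unpooled uncorrected 0.9147, unpooled corrected 0.8774, arcsine 0.9426, log odds ratio 0.8460. The VRI figure alone is less informative, because 93.9% also arises in step 3 from the two-sided test. The one-sided reading rests on the protocol pair matching together.

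**Step 3: power of the planned test.** With n_k per arm, m_k events in LTCF k and a_k of them on NTZ, the statistic is

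(|Σa_k − Σm_k/2| − 0.5)² / ΣV_k, where V_k = n_k² m_k(2n_k − m_k) / [(2n_k)²(2n_k − 1)],

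and the test rejects above the chi-square (1 df) quantile at 1 − alpha. Simulated power, 3,000,000 trials per case, equal strata:

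| LTCFs | COVID-19, 0.049 | COVID-19, 0.047 | VRI, 0.001 |
|---|---|---|---|
| 5 | 0.9018 | 0.9013 | 0.9394 |
| 10 | 0.9026 | 0.9019 | 0.9392 |
| 16 | 0.9027 | 0.9017 | 0.9390 |
| 20 | 0.9023 | 0.9013 | 0.9391 |

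Exact enumeration in a single stratum agrees: 0.9018, 0.9014 and 0.9394. Unequal strata of 8 to 80 subjects give 0.9026, 0.9015 and 0.9390.

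**Step 4: compare with the printed figures.**

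- COVID-19: protocol 92.8 − 90.2 = 2.6 points too high; SAP 90.1 − 87.1 = 3.0 points too low.
- Floors: above 92% fails at each of 5, 10, 16 and 20 LTCFs. Above 87% is true but loose; above 90% holds at all four.
- VRI: the protocol's 93.9% is right; the SAP's 91% is 93.9 − 91 = 2.9 points too low.

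**Step 5: the test as Protocol 8.4.1 words it** (two-sided, no correction stated). COVID-19 at 0.049 is 0.9126 by formula and 0.9418 by simulation with 20 LTCFs. The protocol's 92.8% matches neither.

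**The case against.** The strongest reply is that the protocol mentions no continuity correction. Against the uncorrected two-sided test in Protocol 8.4.1, simulated power is 94.2%, so 92.8% is conservative and the floor above 92% holds. That is correct as far as it goes. However, Protocol 8.4 leaves the detail of the methods to the SAP, and SAP 4.2.1 specifies the correction. The corrected test is the one that will be run, and for it 92.8% is too high.

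A second reply is that the SAP already carries a lower, explicitly two-sided figure and explains when each alpha applies. That helps, but it does not correct the number printed in Protocol 8.1, and the SAP's own figures sit about 3 points below simulation.

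A third reply is that prospective power plays no part in the analysis. This stands, and it limits the weight of the point.

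A reader might also infer more than the documents support:

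- *That the protocol plans one-sided tests, or never states sidedness.* Protocol 8.4.1 says two-sided at exactly 0.049 and 0.001. Only the power statement in 8.1 lacks sidedness.
- *That a one-sided power calculation is established.* It is a close numerical match and needs a correction the protocol never mentions. The formula attributed to the SAP is inferred in the same way.
- *That the SAP figures are the right ones and the protocol's should simply be replaced by them.* For VRI this would replace a correct figure with one about 3 points too low.

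**Conclusion.** The point holds, and Protocol 8.1 is wrong as written on COVID-19 power for the planned test. The two documents give irreconcilable powers for one design, and alpha explains almost none of the difference. For the two-sided, continuity-corrected CMH test, COVID-19 power is about 90.2% at 0.049 and 90.1% at 0.047, which lies between the two printed values. VRI power is 93.9%, as the protocol says.

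N=800 is not undermined: for the planned test, power is at least 87.1% by the conservative normal approximation and about 90% by simulation. A conclusion that the trial is underpowered is not supported.

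These figures assume the documents' own rates, the same rates in every LTCF, independent subjects, and 400 analysed per arm. The conflict between the documents is certain; how each printed figure was obtained is inferred.

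**What to change.** Use one basis in both documents and name it. Simulation of the planned two-sided, continuity-corrected CMH test is preferable.

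- **Protocol 8.1 and SAP 1.3:** state COVID-19 power of about 90.2% at two-sided 0.049 (no interim efficacy review) and 90.1% at two-sided 0.047 (review done), above 90% for 5, 10, 16 or 20 LTCFs, and VRI power of 93.9% at two-sided 0.001. This also supplies the 0.049 case, which SAP 2.4 allows and SAP 1.3 omits.
- **Protocol 8.1:** say that the alphas are two-sided.
- **Protocol 8.1, Protocol 8.4.1 and SAP 1.3:** say that the test is continuity-corrected, as SAP 4.2.1 does.

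If the normal approximation is kept instead, the consistent set is 87.5% (0.049), 87.1% (0.047) and 91.0% (VRI). It should be labelled conservative, since each figure is about 3 points below simulation.

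The cost is wording, plus one simulation to document. Sample size, alpha, data and test do not change. The downside is a slightly less favourable COVID-19 power in the protocol, about 90.2% in place of 92.8%.
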